The sample size is based on clinical considerations to provide sufficient safety information for the analysis of the primary safety objective. With a sample size of N=75 in each ARCT-021 Study Group by Age Cohort or N=75 in pooled placebo recipients by Age Cohort, the probability of observing at least 1 AE for a given true event rate of a particular AE is >99.9% with a sample size of 75 participants for a given true AE rate of 10%.

Analysis Sets:

Intent-to-Treat (ITT) analysis set will include all participants who receive at least 1 dose of priming study vaccine (ARCT-021 or placebo). Participants will be analyzed according to the study vaccine the participant was randomly assigned to at the time of priming or booster vaccination.

Arcturus Therapeutics, Inc.
Protocol ARCT-021-04, Version 6.0

ARCT-021
09 March 2022

The safety analysis set will include all participants who receive at least 1 dose of priming study vaccine (ARCT-021 or placebo). Participants will be analyzed according to the study vaccine actually received at the time of priming or booster vaccination.

The reactogenicity analysis set (RAS) includes all participants who receive any dose of priming study vaccine (ARCT-021 or placebo) and provide at least 1 reactogenicity diary report for the time period evaluated. Participants will be analyzed according to the vaccine received.

The per-protocol analysis set will include all eligible randomized participants who receive the correct assigned dose(s) of study vaccine within the predefined SAP window, have blood collection within the SAP window, have valid immunogenicity results for the relevant time point(s), and have no other major protocol deviations expected to affect immunogenicity, as determined by the Sponsor Medical Monitor in a blinded manner. All participants in the per-protocol analysis set will be analyzed according to the study vaccine that was actually received, in the event of a discrepancy.

The modified intent-to-treat (mITT) analysis set includes all participants who received at least one dose of study vaccine and who have pre- and post-vaccination immunogenicity data evaluable by the assay in use with valid results for the relevant time point(s). The mITT analysis set will be analyzed according to vaccine assigned.

The CMI subset includes all participants who have evaluable pre- and post-vaccination CMI data available. The data sets include: CD4+ T-cell responses (background subtracted), CD8+ T-cell responses (background subtracted), and Th1/Th2 CD4+ T-cell responses (background subtracted).

The Booster Randomized analysis set consists of all participants who are randomized to a booster vaccination, regardless of the participant's study treatment status in the study. Participants will be analyzed according to the study vaccine to which they were randomized for receipt of booster vaccine.

The Booster Safety analysis set includes all participants who receive at least 1 dose of booster study vaccine (ARCT-021, ARCT-154, ARCT-165 or placebo) or have safety data collected in the period following booster administration. If a participant did not receive a booster dose but has safety data collected for the booster vaccination period, the participant will be included in the placebo booster group for summarization. Participants will be analyzed according to the vaccine actually received.

The Booster Reactogenicity analysis set includes all participants who receive any dose of booster vaccination (ARCT-021, ARCT-154, ARCT-165 or placebo) and provide at least 1 diary entry for the time period evaluated. Participants will be analyzed according to the vaccine actually received.

Further details relating to the analysis sets are provided in the SAP.

Statistical Methods:

Safety Analyses:

Numbers and percentages (with 95% confidence intervals [CI]) based on the Clopper-Pearson method) of participants with solicited local and systemic AEs through 7 days after

Arcturus Therapeutics, Inc.
Protocol ARCT-021-04, Version 6.0

ARCT-021
09 March 2022

each vaccination will be summarized by Study Group, Age Cohort and the maximum toxicity grade over 7 days after each vaccination. The duration of solicited local and systemic AEs after each vaccination will also be summarized by Study Group.

Unsolicited AEs will be coded by preferred term and system organ class using the latest version of the Medical Dictionary for Regulatory Activities (MedDRA) and summarized by Study Group, Age Cohort, as well as by severity and relationship to study vaccine. Adverse events through 28 days after each vaccination and all MAAEs, NOCDs, and SAEs through Early Termination Visit will be listed separately and summarized by Study Group and Age Cohort.

Actual values, changes from baseline (where indicated), and toxicity grading for clinical safety laboratory assessment results will be summarized by Study Group and Age Cohort at each time point using descriptive statistics.

Concomitant medications will be summarized by Study Group and Age Cohort by preferred drug name as coded using the World Health Organization drug dictionary.

Additional subgroup analyses are specified in the SAP.

Immunogenicity Analyses:

The primary immunogenicity analyses will be performed using the mITT set evaluating responses measured by neutralizing antibody assay.

For all GMC and GMT calculations (binding and neutralizing antibody responses), geometric means will be calculated as the mean of the assay results after making the logarithm transformation and then exponentiating the mean to express results on the original scale. Two-sided 95% CIs will be obtained by taking natural log transformations of concentrations/titers, calculating the 95% CI with reference to the t-distribution, and then exponentiating the CIs. An analysis of covariance (ANCOVA) model will be constructed at each post-vaccination immunogenicity visit on the log transformed titer, including the study treatment group and age group (≥ 18 to <56 years; ≥ 56 years) as fixed effects and natural log baseline titer as a covariate. Comparisons of ARCT-021 groups vs. placebo will be performed within each post-baseline visit and no adjustments for multiplicity will be carried out. These models will be used to estimate the geometric mean ratios with 95% CIs at each time point comparisons being of primary interest.

The GMFR will be calculated as the mean of the difference of logarithmically transformed assay results (later time point – earlier time point) and exponentiating the mean.

Seroconversion (SC) is defined with as ≥ 2 -fold and also ≥ 4 -fold GMFR. Seropositivity is defined as those participants with undetectable antibody responses at baseline whose antibody responses become detectable at time points after baseline. The number and percentage of participants with ≥ 2 - and 4-fold GMFR from baseline and with seropositivity will be provided with 2-sided 95% CI using the Clopper-Pearson method at each post-baseline time point. The common difference of seroconversion rate and 95% CI between each vaccine dose group and the placebo will be estimated in the mITT using the Cochran–Mantel–Haenszel (CMH) method with stratification factors for each time point from Day 28 and later timepoints as specified in the SAP.

Arcturus Therapeutics, Inc.
Protocol ARCT-021-04, Version 6.0

ARCT-021
09 March 2022

Cell-mediated response for both Th1 and Th2 pathways will be assessed by measuring intracellular cytokine expression by flow cytometry of PBMCs isolated from whole blood and summarized by Study Group and Age Cohort in the CMI analysis set. Further details are described in the SAP.

Exploratory analyses of antibody responses and CMI will be described in the SAP prior to analysis. Additional subgroup analyses are described in the SAP.

Interim Analyses:

Three interim analyses will be performed.

- The first interim analysis will focus on safety and will evaluate available safety data for all participants who were initially enrolled as of 05 February 2021 when they have completed Day 7 or Early Termination visit procedures.
- The second interim analysis will evaluate available safety and immunogenicity data for all participants who were initially enrolled as of 05 February 2021 when they have completed Day 28 or Early Termination visit procedures.
- The third interim analysis will evaluate available safety and immunogenicity data for all participants when they have completed Day 56 or Early Termination visit procedures.

No data base lock will be performed prior to first and second interim analyses, so it is assumed that the data may not be fully monitored or queried. In addition, the datasets from immunogenicity assessments may not contain all participants' data. However, the data cuts outlined above are intended to inform additional clinical development considerations, including selection of ARCT-021 dose for booster administration and selection of final dose and schedule for ARCT-021 administration in the Phase 3 study. The data will be monitored prior to and the database will be locked after the third interim analysis to inform an interim clinical study reporting.

All available safety and immunogenicity data will be summarized. Blinded data will be shared with the SRC and unblinded data will be shared with the DSMB.

At each analysis, the DSMB will review the available data and make recommendations to the Sponsor to continue, modify, or discontinue study enrollment (if the study is enrolling participants). The DSMB will also review safety and, if available, immunogenicity data at each interim analysis.

For dose selection for Phase 3 study use, it is expected that the Sponsor will select the dose on the basis of review of available immunogenicity data and safety data (including DSMB evaluation of the benefit/risk profile). It is anticipated that if one or more vaccine groups have an acceptable safety and immunogenicity profile, the vaccine group with the smallest number of doses will be selected for future use based on the review of the Phase 2 study data. As of protocol version 4.0, the Sponsor has selected single doses of 5 µg ARCT-021 for future use in Phase 3 studies. See the IB for more detail.

LIST OF ABBREVIATIONS

Abbreviation	Definition
ACE-2	angiotensin-converting enzyme-2 receptor
AE	adverse event
AESI	adverse event of special interest
BAb	binding antibody
BMI	body mass index
CESI	clinical event of special interest
CFR	Code of Federal Regulations
CI	confidence interval
CMH	Cochran–Mantel–Haenszel
CMI	cell-mediated immune
COVID-19	Coronavirus Disease 2019
CRF	case report form
CRO	contract research organization
CSR	clinical study report
DSPC	1,2-distearoyl-sn-glycero-3-phosphocholine
DSMB	Data Safety Monitoring Board
EDC	electronic data capture
eCRF	electronic case report form
FDA	US Food and Drug Administration
FSH	follicle-stimulating hormone
GCP	Good Clinical Practice
GMC	geometric mean concentration
GMFR	geometric mean fold-rise
GMR	geometric mean ratio
GMT	geometric mean titer
HIV	human immunodeficiency virus
HCP	healthcare provider
HRT	hormone replacement therapy
IB	Investigator's Brochure
IcEv	intercurrent event
ICF	informed consent form
ICH	International Council for Harmonisation

Abbreviation	Definition
IEC	independent ethics committee
IFN	interferon
IgG	immunoglobulin G
IL	interleukin
IM	intramuscular
IRB	institutional review board
IRT	interactive response technology
ITT	Intent-to-Treat
LLOD	lower limit of detection
LLOQ	lower limit of quantification
LOD	limit of detection
LOQ	limit of quantification
LUNAR®-COV19	LUNAR-COV19 refers collectively to vaccines ARCT-021, ARCT-154, and ARCT-165
MAAE	medically attended AE
MedDRA	Medical Dictionary for Regulatory Activities
mITT	modified intent-to-treat
MMRM	mixed-model repeated measures
MSD	MesoScale Discover
NAb	neutralizing antibody
NOCD	new onset of chronic disease
PBMC	peripheral blood mononuclear cells
PEG2000-DMG	polyethylene glycol-lipid conjugate-1,2-Dimyristoyl-rac-glycero-3-methoxypolyethylene glycol-2000
PPE	personal protective equipment
PRNT	plaque reduction neutralizing titer
RBD	receptor binding domain
RNA	ribonucleic acid
RT-PCR	reverse transcriptase-polymerase chain reaction
SAE	serious adverse event
SAP	statistical analysis plan
SARS-CoV-2	Severe Acute Respiratory Syndrome-Coronavirus-2
SC	Seroconversion
SRC	Safety Review Committee

Arcturus Therapeutics, Inc.
Protocol ARCT-021-04, Version 6.0

ARCT-021
09 March 2022

Abbreviation	Definition
SUSAR	suspected unexpected serious adverse reaction
SWFI	sterile water for injection
TNF	tumor necrosis factor
VAERD	vaccine associated enhanced respiratory disease
VEEV	Venezuela equine encephalitis virus
WHODRUG	World Health Organization Drug Dictionary
WOCBP	women of childbearing potential

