
 To assess the safety and reactogenicity of ARCT-021 compared to placebo for priming vaccination 	
Safety will be evaluated in all participants receiving at least 1 administration of study vaccine (ARCT-021 or placebo) and will be summarized for each vaccination as number and percentage of participants with:
 
 Any unsolicited adverse event (AE) initiating within 28 days after each study vaccine administration, by severity and relationship to study vaccine Any medically attended adverse event (MAAE), new onset of chronic disease (NOCD), AE leading to discontinuation/withdrawal or serious adverse event (SAE) through Early Termination Safety laboratory assessment before and 7 days after each study vaccine administration, by toxicity grade 
Reactogenicity will be evaluated in all participants receiving at least a single administration of study vaccine and will be summarized for each vaccination as number and percentage of participants with:
 
 Any solicited local or systemic AE initiating within 7 days after each study vaccine administration, by toxicity grade

 To assess the neutralizing antibody responses of ARCT-021 compared to placebo for priming vaccination 	
Neutralizing antibody (NAb) responses will be evaluated in all participants receiving at least 1 administration of study vaccine (ARCT-021 or placebo)
 
 Geometric Mean Titer (GMT) measured at all time points Geometric Mean Fold-rise from baseline (GMFR); measured at all time points after baseline (= Day 0) Percentages of participants with ≥ 2- and 4-fold increase in titer from baseline (Seroconversion [SC]); measured at all time points after baseline Geometric Mean Ratio (GMR) of the GMTs (ARCT-021/placebo) measured at all time points

 To select the dose and schedule for use in the Phase 3 study in adult participants 	
Safety and reactogenicity data after each priming vaccine administration and immunogenicity responses measured 28 days after each priming vaccination will be evaluated in younger (18 to < 56 years) and older (≥ 56 years) adults

Secondary	

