4.2 Delaying or Discontinuing Study Treatment and Participant Withdrawal From the Study

4.2.1 Delay in Study Treatment

Body temperature must be measured, and the participant asked about recent antipyretic or analgesic use prior to each administration of study vaccine.

The following events constitute criteria for delay of study vaccination and the window of delay specified forthwith:

- Acute moderate or severe infection with or without fever at the time of dosing (delay: until afebrile for 48 hours and clinically recovered according to Investigator judgment)
 - Participants with minor illness and without fever may be vaccinated if deemed appropriate according to Investigator judgment
- Fever without signs of acute illness, defined as body temperature $\geq 38.0^{\circ}\text{C}$ (100.4°F) (delay: until afebrile for 48 hours)
 - Use of antipyretics or analgesics within 24 hours (delay: at least 24 hours)
Vaccination may be performed once these criteria are no longer met and this will not constitute a protocol deviation.

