7.1 Estimands and Intercurrent Events

Possible intercurrent events are presented in [Table 7-1](#).

Table 7-1 Intercurrent Event Types

Label	Intercurrent Event (IcEv) Type
IcEv1 (Death)	Death due to any cause (including pneumonia) other than COVID-19.
IcEv2 (Missed dose)	Does not receive the second or booster vaccinations at Day 28 and Day 208, respectively.
IcEv3 (Immune-modifying)	Use of immune-modifying drugs or non-study vaccines which interfere with immunogenicity.
IcEv4 (Early infection)	Antigens or antibodies indicating exposure to SARS-CoV-2 prior to vaccination or early infection before Day 7. (This IcEv is particularly relevant to assessing immunogenicity.)
IcEv5 (Study infection)	Develops COVID-19 or asymptomatic SARS-CoV-2 infection on or after Day 7. (This IcEv is particularly relevant to immunogenicity and CESI events.)

Attributes for the primary safety and immunogenicity estimands with strategies for intercurrent events (IcEvs) are presented in [Table 7-2](#).

Table 7-2 Primary Safety and Immunogenicity Estimands With Rationale and Strategies to Address Intercurrent Events

Estimand Label	Estimand 1 (Safety)
Estimand Description	Count and percentage of vaccinated healthy adults who would develop MAAEs, NOCDs, SAEs, AEs leading to discontinuation/withdrawal, solicited AEs, and unsolicited AEs: These will be evaluated after each dose of study vaccine by priming vaccine study group (Group 1, 2, 3, and 4) and by booster vaccine received (ARCT-021, ARCT-154, ARCT-165, or placebo). A treatment policy strategy is used for assessing safety irrespective of an early infection within 7 days after the first vaccination or an infection during the study or missed subsequent vaccination. Infections and death are included in the endpoint (composite strategy).
Target Population	Participants receiving at least 1 dose of study vaccine (as defined by eligibility criteria).
Endpoint	Occurrence of MAAEs, NOCDs, AEs leading to discontinuation/withdrawal, SAEs, solicited, or unsolicited AEs: 
 Solicited AEs within 7 days of each vaccination (by Toxicity Grade, Appendix 13.4): Day 7, Day 35, Day 215 Unsolicited AEs within 28 days of each vaccination (by mild/moderate/severe severity): Day 28, Day 56, Day 236 MAAEs, NOCDs, SAEs, AEs leading to discontinuation/withdrawal from Vaccination 1 to Prior to Vaccination 2, Vaccination 2 to Prior to Booster Vaccination, Overall Prior to Booster Vaccination, and Post-booster Vaccination

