4.4.4. Per-Protocol Analysis Set

The Per-Protocol analysis set includes all eligible randomized participants who receive the correct assigned dose(s) of assigned study vaccine within the predefined window (see Table 4-3), have blood collection with valid immunogenicity results within the predefined window (see Table 4-4) and have no other major protocol deviations expected to affect immunogenicity, as determined by the Sponsor Medical Monitor in a blinded manner.

Table 4-3 Study Vaccine Dosing Windows – Priming Vaccination Period

Visit	Window
Dose 1 Administration (Day 0)	0
Dose 2 (Day 28)	+/- 3 days

Table 4-4 Blood Sampling for SARS-CoV-2 Antibodies and CMI Windows – Priming Vaccination Period

Visit	Window
Day 56	+/- 7 days

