9.1.2.1. Unsolicited AEs through 28 Days Post Each Vaccination

Summaries of unsolicited AEs through 28 days post each vaccination dose will be presented using the following definition:

- **Vaccination 1:** Time period from first vaccination through prior to the second vaccination for participants that received the second vaccination and through 28 days following the first vaccination for participants that did not receive the second vaccination
- **Vaccination 2:** Time period from second vaccination through 28 days following the second vaccination
- **Booster Vaccination:** Time period from booster vaccination through 28 days following the booster vaccination.

The summaries for Vaccination 1 and Vaccination 2 will be by the 4 priming vaccination treatment groups for the priming vaccination period while the summaries for booster vaccination period will be by the 8 priming-booster vaccination treatment groups and for the combined E1+E2+...+G1+G2 and H1+H2 groups (Table 4-1).

For re-enrolled subjects, the above summary for the priming vaccination phase will be repeated.

An overall summary of unsolicited AEs through 28 days post vaccination will be produced for all participants and by age group including the number and percentage of participants with any of the following (including 2 sided 95% CIs using the Clopper-Pearson method):

- Any unsolicited TEAEs
- Any severe unsolicited TEAEs
- Any unsolicited TEAEs that are treatment related

- Any severe unsolicited TEAEs that are treatment related
- Any serious TEAEs
- Any treatment-emergent MAAEs
- Any treatment-emergent NOCDs
- Any TEAEs leading to discontinuation/withdrawal
- Any TEAEs leading to death

In addition, incidence of unsolicited AEs through 28 days post each vaccination will be summarized by SOC and PT including number and percentage of participants with an event for all participants and by age group for the following:

- All unsolicited AEs
- All unsolicited AEs by severity
- All unsolicited AEs by relationship to treatment

For re-enrolled subjects, the above summaries will be repeated for the Safety set. A summary of incidence of unsolicited adverse events up to 28 days post booster vaccination with active boosters pooled will be presented.

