9.1.2.2. Unsolicited AEs by Time Period

Summaries of unsolicited AEs by time period will be presented using the following definition:

- **Prior to Booster Vaccination** summary tables include the following time periods with data summarized by the 4 priming vaccination treatment groups:
 - **Vaccination 1 through prior to Vaccination 2:**

- For participants who receive vaccination 2, this is the time period from first vaccination through prior to second vaccination
- For participants who do not receive vaccination 2 but do receive a booster vaccination, this is the time period from first vaccination through prior to the booster vaccination
- For participants who only received the first vaccination, this is the time period from first vaccination until early termination or end of the priming period (Day 207), whichever is earlier
- **Vaccination 2 through prior to Booster Vaccination:**
 - For participants who receive the booster vaccination, this is the time period from the second vaccination through prior to the booster vaccination
 - For participants who do not receive the booster vaccination, this is the time period from second vaccination until early termination or end of the priming period (Day 207), whichever is earlier
- **Prior to Booster Vaccination - Overall**
 - This is the time period from first vaccination through prior to booster vaccination. For participants who do not receive a booster vaccination, this is the time period from first vaccination through early termination or end of the priming period (Day 207), whichever is earlier.
- **Post Booster Vaccination through Early Termination** summary tables include data summarized by the 8 priming-booster treatment groups as well as a summary for the combined E1+E2+...+G1+G2 and H1+H2 groups. For subjects who do not receive a booster vaccination, this is the time period from the start of the booster period (Day 208) through early termination.
 - An overall summary of unsolicited adverse events post booster vaccination with active boosters pooled (as presented in Table 4-1; e.g., A1, A2, B1, B2, etc.) will also be presented.

The summaries described in [Section 9.1.2.1](#) will be produced by time period and by time period and age group. In addition, the following summaries will be presented by time period and by time period and age group:

- Overall summary and incidence of treatment emergent MAAE
- Overall summary and incidence of treatment emergent NOCDs

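### The primary unsolicited-AE endpoint stops 28 days after each dose, but the SAP's 28-day table counts Dose 1 events up to Dose 2 with no 28-day cap for those who receive it

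*Protocol*

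**What the plan says.** The endpoint is worded identically in the Protocol Synopsis, Protocol Table 2-1 and SAP Table 2-1: "Any unsolicited adverse event (AE) initiating within 28 days after each study vaccine administration, by severity and relationship to study vaccine". Estimand 1 (Protocol Section 7.1) repeats the limit and names the matching visits: "Unsolicited AEs within 28 days of each vaccination (by mild/moderate/severe severity): Day 28, Day 56, Day 236".

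SAP Section 9.1.2.1, whose title also refers to 28 days after each vaccination, defines the periods as follows:

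- Vaccination 1, Dose 2 received: "Time period from first vaccination through prior to the second vaccination for participants that received the second vaccination".
- Vaccination 1, Dose 2 not received: "through 28 days following the first vaccination for participants that did not receive the second vaccination".
- After Dose 2, the rule is a fixed length: "Time period from second vaccination through 28 days following the second vaccination". The booster period is built the same way.

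SAP Section 9.1.2.2, which tabulates AEs by longer periods, uses this for its Dose 1 period: "For participants who receive vaccination 2, this is the time period from first vaccination through prior to second vaccination".

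On the timing of Dose 2, SAP Table 4-3 gives "Dose 2 (Day 28) +/- 3 days", but only as a condition of the Per-Protocol set. The unsolicited-AE tables use the Safety set. Protocol Section 4.2.1 delays a dose for infection, fever or recent antipyretic or analgesic use, states no maximum, and adds: "Vaccination may be performed once these criteria are no longer met and this will not constitute a protocol deviation".

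SAP Section 1 says that the SAP prevails where it differs from the protocol. SAP Section 11 lists four changes from the planned analysis; this is not one of them.

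**The concern.** A table presented as 28-day incidence after Dose 1 would contain events that start later than 28 days whenever Dose 2 is given after Day 28. Its Dose 1 column would mix two rules: a fixed 28 days for participants who stop after Dose 1, and a variable length for the rest. The Dose 2 and booster columns are fixed at 28 days, so reading across doses compares periods of different length.

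This touches a primary endpoint. Safety after each priming dose also feeds the primary objective on dose and schedule, although Protocol Section 7.8 records that the Phase 3 dose has already been chosen. What remains at stake is whether the final report's Dose 1 rates are what their label says.

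**Working it through.** **1. The plan's own figure.** The documents give no figure for this window. Their one AE calculation (Protocol Table 7-3, SAP Table 4-2) uses p = 1 − (1 − R)^N. With R = 0.01 and N = 75, p = 1 − 0.99^75 = 0.5294, which matches the stated 52.9%. It assumes no period of observation, so it neither supports nor contradicts what follows.

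**2. Length of the Dose 1 period under SAP Section 9.1.2.1.**

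| Participant | Days counted | Relative to 28 |
|---|---|---|
| Dose 2 on Day 25 | 25 | 25/28 = 0.893 |
| Dose 2 on Day 28 | 28 | 1.000 |
| Dose 2 on Day 31 | 31 | 31/28 = 1.107 |
| Delay of 7 days (assumed) | 35 | 1.250 |
| Delay of 14 days (assumed) | 42 | 1.500 |
| Delay of 28 days (assumed) | 56 | 2.000 |
| No Dose 2 | 28 | 1.000 |

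The documents give no distribution of Dose 2 timing, so the delays are illustrations.

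**3. Is the capped rate produced elsewhere?** For Dose 2 recipients, the Section 9.1.2.2 Dose 1 period is the same interval as in Section 9.1.2.1. No planned table therefore applies a 28-day limit to someone dosed after Day 28. For someone dosed on or before Day 28, the two rules give the same result.

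**4. Effect within the visit window.** Assume a constant event rate and a true 28-day risk r (not given in the documents; 10% and 30% are used as a range). Risk over d days = 1 − (1 − r)^(d/28).

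- r = 10%: 25 days gives 8.98%, 31 days gives 11.01%.
- r = 30%: 25 days gives 27.27%, 31 days gives 32.62%.

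If Dose 2 timing were symmetric about Day 28, these would nearly cancel: (8.98 + 11.01)/2 = 10.0%.

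**5. Effect at group level.** Let a fraction f be delayed by D days and the rest be dosed on Day 28. Tabulated rate = (1 − f)·r + f·[1 − (1 − r)^((28 + D)/28)].

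- r = 0.10, f = 0.05, D = 7: 0.95 × 0.10 + 0.05 × 0.1234 = 0.101.
- r = 0.10, f = 0.20, D = 28: 0.80 × 0.10 + 0.20 × 0.190 = 0.118.
- r = 0.30, f = 0.05, D = 7: 0.95 × 0.30 + 0.05 × 0.3597 = 0.303.
- r = 0.30, f = 0.20, D = 28: 0.80 × 0.30 + 0.20 × 0.510 = 0.342.

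**6. Which rows this applies to.** The calculation treats delay as unrelated to having had an event. That can fit a scheduling delay, or a dosing pause under Protocol Section 4.2.5 prompted by someone else's event. It does not fit delay caused by the participant's own new illness. Under Protocol Section 6.4.1.2 such an illness is itself an unsolicited AE, and SAP Sections 9.1.2 and 9.1.2.1 count a participant once per level of summary. That participant is normally already in the any-AE row. The extra days can add new system organ class or preferred term rows, a higher maximum severity or a stronger relationship, but not a second count in the any-AE row.

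**The case against.** The best defence is that the SAP rule is written openly and follows the visit structure. Estimand 1 ties the first period to Day 28, which is the Dose 2 visit, and assigning everything before Dose 2 to Dose 1 leaves no gap. The analysis is descriptive with no hypothesis test, the rule is the same in all four arms, and all unsolicited AEs are listed. Most of this stands and limits the size of the problem. It does not remove the mismatch: the estimand still says within 28 days, participants without Dose 2 are cut at 28 days in the same column, and Section 9.1.2.2 already leaves no gap.

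Three stronger readings are tempting, and the documents do not support them.

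- *Illness that delays Dose 2 inflates the any-AE rate by giving sick participants more time.* Such participants are normally already counted in that row, once. The point is confined mainly to the term, severity and relationship rows.
- *Events in the extra days are collected differently because diary prompts stop at 28 days.* The Synopsis says prompts for all unsolicited AEs run through 28 days after each vaccination. Protocol Section 6 says through 28 days after the last priming and booster vaccinations, which would leave no gap before a late Dose 2. The two statements conflict, so the question is unresolved.
- *The endpoint is never produced for Dose 2 recipients.* It is wrong only for those dosed after Day 28.

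**Conclusion.** The mismatch holds on the text. For participants given Dose 2 after Day 28, the SAP's Dose 1 table includes events beyond the primary endpoint's 28 days, no other planned table gives the capped rate, and the departure is not declared.

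The effect is probably small. Within the visit window the period differs from 28 days by at most 3 days (10.7%) either way. Under the assumed delays (5% to 20% of participants, 7 to 28 days, constant event rate, delay unrelated to prior events), the tabulated rate rises by about 0.1 to 1.8 percentage points from a true 10%, and by about 0.3 to 4.2 points from a true 30%. If onsets become rarer with time since vaccination, the rise is smaller.

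Comparisons of Dose 1 with Dose 2 rates are affected directly. The comparison of ARCT-021 with placebo is distorted only if Dose 2 delays differ by arm, and the documents give no evidence either way.

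**What to change.** In SAP Section 9.1.2.1, define Vaccination 1 for all participants as running from the first vaccination through the earlier of 28 days after it and just before the second vaccination. Events after 28 days but before Dose 2 stay in the Section 9.1.2.2 period table, which repeats the same summaries, so none is lost. The cost is one line of SAP text and one date cap in the program.

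Participants dosed early will still have 25 to 27 days before Dose 2; a table footnote can say so. If the rule is kept as it is, list it in SAP Section 11 and retitle the Dose 1 column. Separately, reconcile the Synopsis and Protocol Section 6 on how long all unsolicited AEs are prompted for, and state in the report which was followed.
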